5.8 Interim Analysis

N/A

6 STUDY MEDICATION (STUDY DEVICE OR OTHER STUDY INTERVENTION)

6.1 Description

STX209 (arbaclofen) is a selective GABA-B receptor agonist. STX209 augments GABA-ergic activity, inhibits presynaptic release of glutamate, inhibits postsynaptic transmission, and modulates intracellular signaling (Isaacson and Hille [3]; Scanziani, Capogna et al. [4]). STX209 is the active isomer of racemic baclofen, an approved GABA-B agonist. Baclofen has demonstrated efficacy in treating hyperactivity and audiogenic seizure phenotypes in the fragile X knockout mouse (Pacey, Heximer et al. [5]). Through elevation of GABA-ergic inhibitory activity, STX209 may act to alleviate ASD symptoms associated with social anxiety and emotional hyperarousal.

6.1.1 Packaging

Tablets are packed and labeled in blister strips of 7 tablets with expiry dates listed on the labels.

6.1.2 Labeling

Tablets are packed and labeled in blister strips of 7 tablets with expiry dates listed on the labels.

6.1.3 Dosing

This is a study examining the acute effect of STX209 on brain activity at two different doses: 15mg and 30 mg. Subjects will receive STX209 via oral disintegrating tablets, administered in individual 15 mg tablets. Over a period of three visits, participants will randomly receive a single-dose of Placebo and in order of smallest to largest a single-dose of STX209 (15mg, and 30mg).

Dosage	Tablets Administered
15mg	One 15mg tablets STX209 and one placebo
30mg	Two 15mg tablets STX209 and no placebo
Placebo	Zero STX209 tablets and two placebo

Across the three visits, all subjects will receive all doses, with the subject and the study investigators blind to dose until the close of the study.

6.1.4 Treatment Compliance and Adherence

Participants are asked to undergo imaging with *three* different dosages (15mg, 30mg, and placebo). Imaging is obtained weekly. If a subject misses an appointment they will be asked to come the following week. The dosage order for that subject will be maintained. If a subject does not complete the entire study the imaging data that was obtained from that subject will be included in the analyses.

6.1.5 Drug Accountability

Adequate records of study drug receipt and disposition will be maintained by the CHOP Pharmacy. Records of receipts, investigational drug orders, dispensing records, and disposition forms will be examined during the course of the study. The purpose of these records is to ensure regulatory authorities and the Sponsor that the investigational new drug will not be distributed to any person who is not a study subject under the terms and conditions set forth in this protocol. The study medication is to be prescribed by the Investigator or designee and may not be used for any purpose

other than that described in this protocol. At study completion, all drug supplies including partially used and empty containers must be returned to Sponsor or designee.

7 SAFETY MANAGEMENT

Clinical adverse events (AEs) will be monitored throughout the study.

Subject safety will be monitored by adverse events, blood draw, vital signs, and physical examination findings and concomitant medication usage.

[name] or the developmental behavioral pediatrician on call, will be on call during all MEG exams. Specifically, [name] will review pre-MEG vital signs (either in person or over the phone) prior to medication administration. [name] will administer the SMURF and evaluate the vital sign pre-and post-MEG in person for the initial and final study visits. For the visits in between SMURF and vital signs pre- and post-MEG will be done by an approved study staff and [name] will be on call to evaluate the results.

All tests will be promptly reviewed by one of the psychologists on the study team. Any clinical significant findings will be verbally reported to the parent-- either in person during the study visit or later via telephone, depending on when the concern is identified. Parents will be provided with mental health services referrals or will be advised to take their child to a hospital emergency room in the event of an acute care concern.

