5.1.3 Physical Examination

[name] will perform the physical examination (screening visit and visit 3) at the Clinical and Translational Research Center located at [name] or at Main Hospital. However, for the imaging visits (visit 1-visit 3) the SMURF will be performed at the Department of Radiology to assess for adverse events. This can be performed by either [name] or a trained research staff under the guidance and supervision of [name].

- 1) *Physical Examination: A Physical examination will be performed at Screening and at Visit 4. Physical examination findings will be classified using the standard categories listed on the CRF. A brief physical examination will be performed at screening visit and visits 1 through 3 and will include abdominal palpation to assess for liver enlargement, assessing for decreased tone and postural problems, increased drooling and poor orofacial tone, problems holding head up, and difficulty with coordination of motor actions. Any physical examination finding that is judged by the Investigator as a clinically significant change (worsening) from screening visit will be considered an AE, assessed and recorded on the CRF.*
- 2) *Height and Weight: Height and weight measurements must be performed without shoes on, and with only a single layer of light clothing. Height and weight measurements should be performed using consistent units (US).*
- 3) *Medical/Surgical History Review: The study doctor will review Medical/Surgical History*
- 4) *Safety Monitoring Uniform Report Form (SMURF): The SMURF contains a general inquiry, several questions about daily activities (e.g., sleep, appetite, energy level, bowel and bladder function). The general inquiry includes an open ended question about any problems or complaints, as well as questions regarding the need for other medications and doctor or health care encounters since the last study visit. The next section includes 20 to 25 specific queries. These items are rated as not present, mild, moderate or severe. The ratings mild, moderate, or severe are defined as follows: mild=present, but no intervention required; moderate=present, may be bothersome or may require intervention; severe=present, bothersome and requires intervention. The last section includes specific questions about daily activities. All new adverse events (mild, moderate, or severe) will be documented. The status of previously reported adverse events will be monitored as well.*

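### Section 5.1.3 requires a brief physical exam at every imaging visit, but Table 1 and 5.2.1 schedule one only at Screening and Visit 3, so a site following the schedule would examine nobody on 15 mg

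*Combined protocol and SAP*

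**What the plan says.** Section 7 counts examination among the safety tools: "Subject safety will be monitored by adverse events, blood draw, vital signs, and physical examination findings and concomitant medication usage". Section 5.1.3, item 1 fixes when and what: "A brief physical examination will be performed at screening visit and visits 1 through 3". The content is abdominal palpation plus "assessing for decreased tone and postural problems, increased drooling and poor orofacial tone, problems holding head up, and difficulty with coordination of motor actions". A finding "judged by the Investigator as a clinically significant change (worsening) from screening visit will be considered an AE".

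Other places give a different schedule:

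- Table 1 marks the physical exam at Screening and Visit 3 only.
- Section 5.2.1 gives it 15 minutes at Visit 3, after the post-drug MEG, and has no such line at Visits 1 or 2.
- Section 4.3 lists vital signs, MEG, MRI/MRS and the SMURF at the imaging visits, but no exam.
- Sections 3.3.2 and 4.7 refer to an exam or medical evaluation at Visit 3.
- The opening sentence of 5.1.3 names Screening and Visit 3. Item 1 then puts a physical exam at Screening and Visit 4, although Table 1 has no Visit 4.

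On who is present, Section 7 has the physician do the SMURF and evaluate vital signs in person at the initial and final visits, and then says: "For the visits in between SMURF and vital signs pre- and post-MEG will be done by an approved study staff". The physician "or the developmental behavioral pediatrician on call, will be on call during all MEG exams".

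**The concern.** The protocol gives incompatible instructions for a safety procedure in adolescents receiving single doses of 15 mg and 30 mg. Site staff usually work from the schedule table and the visit lists, so the instruction in 5.1.3 is the one most likely to be lost.

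Which doses then go unexamined depends on the dose orders. Because 15 mg must precede 30 mg, 15 mg cannot fall at Visit 3, the only on-study visit with a scheduled exam. A clinically significant worsening on examination is an adverse event under 5.1.3, and adverse events are a secondary endpoint under 5.5. An examination sign that nobody looks for is not recorded.

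**Working it through.** The plan states no figure on this point, so there is none to reproduce. The check crosses the dose orders with the exam schedule.

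**Inputs.** Dose orders: 3.2. Exam schedule: Table 1 and 5.2.1, against 5.1.3 item 1. Subjects: 40 (3.3.2). Visit spacing: at least four days (note to Table 1). Half-life of STX209 from the orally disintegrating tablet: 5.85 h (1.3.1.2). Allocation ratio: not stated, so 1:1:1 is assumed. The 8.1.1 table repeats the 3.2 grid under visit headings; read across, it would give some subjects the same dose twice, so the option labels in 3.2 are used.

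**Step 1: dose at each visit.**

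| | Option 1 | Option 2 | Option 3 |
|---|---|---|---|
| Visit 1 | placebo | 15 mg | 15 mg |
| Visit 2 | 15 mg | placebo | 30 mg |
| Visit 3 | 30 mg | 30 mg | placebo |

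**Step 2: doses followed by an exam.** Each option has 40/3 = 13.3 subjects.

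| Dose | Following Table 1 and 5.2.1 (Visit 3 only) | Following 5.1.3 item 1 (Visits 1 to 3) |
|---|---|---|
| 15 mg | 0 of 40 | 40 of 40 |
| 30 mg | 2 × 13.3 = 26.7 of 40 (67%) | 40 of 40 |
| Placebo | 13.3 of 40 (33%) | 40 of 40 |
| Active doses together | 26.7 of 80 (33%) | 80 of 80 |

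The right-hand column assumes the exam is done after dosing, a timing that 5.1.3 does not give. The zero for 15 mg holds under any allocation. The Option 3 count depends on the ratio: under simple randomisation with probability 1/3, the 2.5th and 97.5th percentiles of Binomial(40, 1/3) are 8 and 19.

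**Step 3: can the Visit 3 exam stand in for an earlier dose?** Four days is 96 h, and 96/5.85 = 16.4 half-lives. The fraction remaining is 0.5^16.4 = 1.15 × 10⁻⁵, about 0.001%. An exam at Visit 3 says nothing about acute signs of a dose given at Visit 1 or 2.

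**Step 4: what remains at Visits 1 and 2 without the exam.** Vital signs, the SMURF and adverse event assessment are scheduled at every imaging visit. The physician reviews vital signs before dosing, and a physician is on call. As 5.1.3 describes it, the SMURF is a set of questions with severity ratings, so it is not itself an examination of tone or coordination.

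**The case against.** The strongest reply is that the protocol already requires the exam. Item 1 of 5.1.3 can be read as two tiers: a full examination at entry and close-out (Visit 4 meaning the fourth visit overall, which is Visit 3 in Table 1), and a brief drug-sign examination at Screening and every imaging visit. On that reading the row in Table 1, the 5.2.1 entry and the final exam in 4.7 describe the full examination. The matching content of the Screening exam in 3.1.2 and 4.2 is then expected, because the brief exam is done at Screening too. The lists are also incomplete elsewhere: Section 7 wants vital signs before and after MEG, but 5.2.1 shows them once per visit.

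This stands, and it is the better reading. It places the error in the schedule. It does not remove the error, since the brief exam has no row, no time slot and no named examiner at Visits 1 and 2.

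Three stronger inferences are tempting and are not supported:

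- **That a physician must attend Visit 2 in person because 30 mg can fall there.** Section 7 appears to assign on-call cover deliberately, with review of vital signs before dosing and physician evaluation of the staff's results. Section 5.1.3 says of the SMURF "This can be performed by either" the physician or supervised trained staff. Attendance around both MEG scans would also take far more time than one examination.
- **That 30 mg is shown to be hazardous without the exam.** It is twice the largest single STX209 dose reported in 1.3.1.1 (15 mg). But the same section reports up to 45 mg in a day without significant safety or tolerability effects, and two small adult studies of 50 mg racemic baclofen with mild effects or slight tiredness that did not interfere with procedures. Section 8.4.2 puts neuromuscular weakness at under 1% in STX209 studies; read as a per-subject rate, that is fewer than 0.01 × 40 = 0.4 expected cases. The protocol calls the dose order an FDA requirement, but does not say that an exam between doses was the reason.
- **That uneven examination biases a comparison of adverse events between doses.** Section 5.6.4 specifies summaries by type, body system, severity and relationship, and no test by dose.

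**Conclusion.** The point holds as a conflict between 5.1.3 and the schedule, with a definite consequence if the schedule is followed: no subject examined on 15 mg, and Option 3 subjects never examined on an active dose. The first result needs only the orders in 3.2. The second covers about a third of subjects, 13.3 of 40, if allocation is equal.

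The documents do not show that the exams would be omitted; that depends on which text the site follows. The matter is worth correcting because it changes what is done for adolescents at each dose. It is modest in weight: the other safeguards apply at every imaging visit, and neither the MEG endpoints nor the sample size is touched.

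**What to change.** 1. Add a brief-exam row to Table 1 at Screening and Visits 1, 2 and 3. Add the exam to 4.3 and to the 5.2.1 lists for Visits 1 and 2, after the post-drug MEG, where 5.2.1 already puts it at Visit 3. Let the final exam at Visit 3 include the brief items, so that visit needs no extra time.
2. State in 5.1.3 who performs it at each visit, and that it follows the post-drug MEG.
3. Correct Visit 4 to Visit 3 in 5.1.3, and make its opening sentence consistent with item 1.
4. Optionally, reconcile the synopsis, which gives all safety evaluations to the study physician, with Section 7, which lets staff do some of them. The on-call arrangement can stay.

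**Cost.** 15 minutes × 2 visits × 40 subjects = 1,200 minutes, or 20 examiner hours, over a study expected to last one year. For subjects, Visit 1 goes from 4 h 50 min to 5 h 05 min and Visit 2 from 4 h 10 min to 4 h 25 min. Section 5.1.3 already implies this time. Doses, orders, blinding and imaging are unchanged.

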7.1 Adverse Event Reporting

The risks to potential participants are expected to be minimal and precautions will be taken to minimize all risks. All unanticipated problems related to research events will be reported to the IRB. A log of all unexpected adverse events will be kept at the study coordinators office for tracking these events and the potential impact on the participants and study.

7.2 Definition of an Adverse Event

An adverse event is any untoward medical occurrence in a subject who has received an intervention (drug, biologic, or other intervention). The occurrence does not necessarily have to have a causal relationship with the treatment. An AE can therefore be any unfavorable or unintended sign (including an abnormal laboratory finding, for example), symptom, or disease temporally associated with the use of a medicinal product, whether or not considered related to the medicinal product.

All AEs (including serious AEs) will be noted in the study records and on the case report form with a full description including the nature, date and time of onset, determination of non-serious versus serious, intensity (mild, moderate, severe), duration, causality, and outcome of the event.

7.3 Definition of a Serious Adverse Event (SAE)

An SAE is any adverse drug experience occurring at any dose that results in any of the following outcomes:

- death,
- a life-threatening event (at risk of death at the time of the event),
- requires inpatient hospitalization or prolongation of existing hospitalization,
- a persistent or significant disability/incapacity, or
- a congenital anomaly/birth defect in the offspring of a subject.

Important medical events that may not result in death, be life-threatening, or require hospitalization may be considered a serious adverse drug event when, based upon appropriate medical judgment,

they may jeopardize the subject and may require medical or surgical intervention to prevent one of the outcomes listed in this definition.

A distinction should be drawn between serious and severe AEs. A severe AE is a major event of its type. A severe AE does not necessarily need to be considered serious. For example, nausea which persists for several hours may be considered severe nausea, but would not be an SAE. On the other hand, a stroke that results in only a limited degree of disability may be considered a mild stroke, but would be an SAE.

7.3.1 Relationship of SAE to study drug or other intervention

The relationship of each SAE to the study intervention should be characterized using one of the following terms in accordance with CHOP IRB Guidelines: definitely, probably, possibly, unlikely or unrelated.

7.4 IRB/IEC Notification of SAEs and Other Unanticipated Problems

The Investigator will promptly notify the IRB of all on-site unanticipated, serious Adverse Events that are related to the research activity. Other unanticipated problems related to the research involving risk to subjects or others will also be reported promptly. Written reports will be filed using the eIRB system and in accordance with the timeline below. External SAEs that are both unexpected and related to the study intervention will be reported promptly after the investigator receives the report.

Type of Unanticipated Problem	Initial Notification (Phone, Email, Fax)	Written Report
Internal (on-site) SAEs Death or Life Threatening	24 hours	Within 2 calendar days
Internal (on-site) SAEs All other SAEs	7 days	Within 7 business days
Unanticipated Problems Related to Research	7 days	Within 7 business days
All other AEs	N/A	Brief Summary of important AEs may be reported at time of continuing review

7.4.1 Follow-up report

If an SAE has not resolved at the time of the initial report and new information arises that changes the investigator's assessment of the event, a follow-up report including all relevant new or reassessed information (e.g., concomitant medication, medical history) should be submitted to the IRB. The investigator is responsible for ensuring that all SAE are followed until either resolved or stable.

7.5 Investigator Reporting of a Serious Adverse Event to Sponsor

Reporting must be consistent with regulatory, sponsor or GCRC requirements (if applicable)

8 STUDY ADMINISTRATION

8.1 Treatment Assignment Methods

8.1.1 Randomization

Across three visits, participants will be randomly assigned a single dose of placebo and in order of smallest to largest a single dose of STX209 (15mg, 30mg). Upon entry into the study, the study pharmacist will assign each subject to one of the below dosage orders, and at each visit providing the research coordinator with the needed pills for that particular visit.

Imaging Assessment 1 Visit 1	Imaging Assessment 2 Visit 2	Imaging Assessment 3 Visit 3
Placebo	15mg	15mg
15mg	Placebo	30mg
30mg	30mg	Placebo

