1.4 Selection of Drugs and Dosages

This is a study examining the acute effect of STX209 on brain activity at two different doses: 15mg and 30mg. Subjects will receive STX209 via oral disintegrating tablets, administered in individual 15mg tablets. Over a period of three visits, participants will receive a single randomly administered dose of placebo and in order from smallest to largest a single-dose of STX209 (15mg, and 30mg). All visits subjects will receive two tablets in the following order, with placebo randomly administered:

Dosage	Tablets Administered
15mg	One 15mg tablet of STX209 and one placebo
30mg	two 15mg tablets STX209 and zero placebo
Placebo	Zero STX209 tablets and two placebo

Across the three visits, all subjects will receive all doses, with the subject blind to dose.

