3.2 Blinding

Across three visits, participants will be randomly assigned a single dose of placebo, and in order from smallest to largest a single-dose of STX209 (15mg, and 30mg). Participants will be blind to dosage order. Clinical Research Associates, LLC (CRA) will provide the needed STX209 tablets and identical placebo tablets. For each subject, the pharmacist at CHOP will create three 2-pill combinations. Order of the STX209/placebo conditions will differ for each subject. Upon entry into the study, the study pharmacist will assign each subject to one of the below dosage orders, and at each visit providing the research coordinator with the needed pills for that particular visit.

Option 1	Option 2	Option 3
Placebo	15mg	15mg
15mg	Placebo	30mg
30mg	30mg	Placebo

Subjects will receive study drug regimen in increasing dosage from smallest to largest and a randomly administered single-dose of placebo.

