5.7 Sample Size and Power

Forty individuals with ASD (aged 14 to 18 years) will be recruited. In each individual, baseline and post acute-dose imaging data will be obtained at three doses: (1) placebo, (2) STX209 15 mg, or (3) STX209 30 mg. Imaging measures at these three doses will be obtained at least 1 week apart, with the order of placebo and STX209 pseudo-randomized with the constraint that the STX209 15mg dose will be administered before the STX209 30 mg dose (FDA requirement). Assuming lost data or incomplete data sets from 4 individuals, the following power calculations were performed assuming a final sample of 36. As detailed in Section 1.3, given significant between subject variability in auditory cortex neural circuit pathology and thus potential between subject differences with regard to normalization of brain activity in response to STX209, the below statistical analyses conservatively assume a response to STX209 from approximately 50% of the participants. As detailed below, although the study is sufficiently powered to assess a baseline versus a 'general' post acute-dose change (i.e., averaging 15mg and 30mg), there is insufficient data to determine if the study is powered to observe a difference between STX209 15mg and STX209 30mg acute dose brain responses. As such, present data will provide preliminary data to guide future studies investigating STX209 dose differences.

Regarding the primary aims, assuming baseline to post acute-dose changes in M100 latency of approximately 2.5 ms (5 ms = one-half the ASD and control group differences reported in Roberts et al. (2010) and in the range observed in the single Arbaclofen study patient (2-8ms), but half of 5 ms given acute responses in only 50% of the participants), and assuming a standard deviation of similar size (which may be conservative given initial cross-dose averaging), and assuming a response in only 50% of the population, given a sample of 36 and $p = 0.05$, the power to detect a main effect on M100 latency is equal to 0.80. Assuming baseline to post acute-dose changes in post-stimulus gamma-band activity approximately half that reported in Edgar et al. (2015), the power to detect a main effect on gamma activity is approximately 0.70.

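### The allocation table in 8.1.1 heads its columns as visits instead of options, so two of its three rows read as dose orders the protocol does not allow

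*Combined protocol and SAP*

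**What the plan says.** The allocation rule is the same wherever the combined protocol and SAP states it in words.

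- Section 8.1.1, above the table: "participants will be randomly assigned a single dose of placebo and in order of smallest to largest a single dose of STX209 (15mg, 30mg".
- Section 3.2, below its own table: "Subjects will receive study drug regimen in increasing dosage from smallest to largest and a randomly administered single-dose of placebo".
- Section 5.7 describes a pseudo-randomised order "with the constraint that the STX209 15mg dose will be administered before the STX209 30 mg dose (FDA requirement".
- Section 6.1.3: "Across the three visits, all subjects will receive all doses". Section 1.4 says the same.

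Sections 3.2 and 8.1.1 both direct the pharmacist in the same terms: "Upon entry into the study, the study pharmacist will assign each subject to one of the below dosage orders". Each then prints a three-by-three table with identical cells in identical positions. In 3.2 the columns are headed Option 1, Option 2 and Option 3. In 8.1.1 the first column is headed "Imaging Assessment 1 Visit 1", and the second and third are headed correspondingly for Visits 2 and 3.

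**The concern.** Under visit headings, a row is one subject's sequence over the three visits. Under option headings, a column is. The cells were laid out for the second reading and carry headings for the first.

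This matters because 8.1.1 is the Randomization section, and its table is what the pharmacist is told to assign from before supplying tablets visit by visit. Someone dispensing by visit would naturally use visit headings. A misallocation might also go unnoticed by others: two tablets are given at every visit, the placebo is identical, and 6.1.3 blinds subject and investigators until the close of the study. Under 6.1.4 an assigned order is kept after a missed visit.

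Two consequences would follow for a subject dosed by the wrong row:

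- **Safety.** Row 3 removes the 15 mg visit before 30 mg. Row 1 does not reverse the order; it only omits 30 mg.
- **Information.** A subject on row 1 or row 3 gives no within-subject comparison of 15 mg with 30 mg, which bears on the dose question in objective 1 of section 2.1.

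**Working it through.** The plan states no figure to reproduce here. The check compares the table with the written rule.

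**Inputs.** The nine cells are from 3.2 and 8.1.1. The rule (each of placebo, 15 mg and 30 mg once, with 15 mg before 30 mg) is from 8.1.1, 3.2, 5.7, 6.1.3 and 1.4. Tablets per dose are from 1.4: placebo has 0 active, 15 mg has 1 active ("One 15mg tablet of STX209 and one placebo"), and 30 mg has 2 active, with two tablets at every visit.

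**Step 1: permitted orders.** Three treatments can be ordered in 3! = 6 ways. In half of these 15 mg precedes 30 mg, which leaves 3: P/15/30, 15/P/30 and 15/30/P (P = placebo).

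**Step 2: the 8.1.1 table read as headed.**

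| Row | Visit 1 | Visit 2 | Visit 3 | Permitted? |
|---|---|---|---|---|
| 1 | P | 15 | 15 | No: 15 mg twice, no 30 mg |
| 2 | 15 | P | 30 | Yes |
| 3 | 30 | 30 | P | No: 30 mg twice, no 15 mg, 30 mg first |

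One of three rows is permitted.

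**Step 3: the same cells read down, as in 3.2.** Column 1 is P/15/30, column 2 is 15/P/30 and column 3 is 15/30/P. All three are permitted, and they are the complete set from step 1.

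**Step 4: distance from a correct visit layout.** Transposing the table gives rows P/15/30, 15/P/30 and 15/30/P. The printed table differs in 2 of 9 cells: row 1 Visit 3 (15 printed, 30 correct) and row 3 Visit 1 (30 printed, 15 correct).

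**Step 5: tablets.** Each subject takes 2 × 3 = 6 tablets.

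| Sequence | Active tablets | Placebo tablets | Total STX209 |
|---|---|---|---|
| Any permitted order | 0 + 1 + 2 = 3 | 3 | 3 × 15 = 45 mg |
| Row 1 as headed | 0 + 1 + 1 = 2 | 4 | 2 × 15 = 30 mg |
| Row 2 as headed | 1 + 0 + 2 = 3 | 3 | 45 mg |
| Row 3 as headed | 2 + 2 + 0 = 4 | 2 | 4 × 15 = 60 mg |

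A completer's total of 2 or 4 active tablets would point to row 1 or row 3. A total of 3 does not establish the order: 30/15/P also uses 2 + 1 + 0 = 3.

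**The case against.** The best case against giving this weight is that the document corrects itself. Section 3.2 carries the same instruction to the pharmacist with the right labels. The sentence just above the 8.1.1 table rules out rows 1 and 3 on sight. Section 8.1.2 has the pharmacist make up three two-tablet combinations per subject, and 1.4 defines exactly three. A pharmacist would have to overlook all of this to dose by the rows. That argument stands as far as intent and likelihood go: misassignment is possible, not expected. It does not make the table harmless, because it sits in the section that governs allocation and conflicts with a constraint the plan attributes to the FDA.

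A second objection is that the table may have been damaged when the PDF was converted to text. Every cell would be right if Visit 1 to Visit 3 were row labels. The visit headings are complete and legible, sit in a header row and do not appear in the 3.2 table, so a conversion fault is unlikely. Only the page itself can exclude it.

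Three stronger readings are tempting, and the documents do not support them:

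- A reader might infer that the trial is designed to give some subjects 30 mg first. The text of 3.2, 5.7, 6.1.3 and 8.1.1 says otherwise.
- A reader might infer that the tablet table in 1.4 is also wrong. It is correct; it only maps doses to tablets and has no visit or option headings.
- A reader might infer that 30 mg exposure is itself the hazard created by the slip. Every subject receives 30 mg in the intended design. What row 3 loses is the earlier 15 mg visit.

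**Conclusion.** The point holds as an internal inconsistency: a labelling error in a dosing instruction. As headed, two of the three rows in 8.1.1 are not permitted, and one of those breaks the stated requirement of 15 mg before 30 mg. The intended orders can be recovered without doubt from 3.2 and the surrounding text, so the design is not at fault.

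No power or sample-size figure changes, and nothing in the documents shows that any subject was or will be misdosed, so no number of affected subjects can be given. The conclusion assumes that the visit headings are column headings on the source page. The table should be corrected because it is an operative instruction and correction costs almost nothing.

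**What to change.** Make one of two changes in 8.1.1:

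- head the columns Option 1, Option 2 and Option 3, and label the rows Visit 1, Visit 2 and Visit 3 (the 3.2 table has no row labels, so copying its headings alone would leave the visits implicit); or
- keep the visit headings and change row 1 Visit 3 to 30 mg and row 3 Visit 1 to 15 mg.

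Then keep a single table and have the other section refer to it.

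If dosing has started, the pharmacist should check the dispensing records kept under 6.1.5 by visit and date, not only by total tablets. The check should confirm that each subject who completed the three visits received all three doses and that 15 mg came before 30 mg.

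The cost is a few labels or two cells, plus a records check if dosing is under way. No patients, visits or procedures are added.
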